recurrence of AF. In the presence of 2-HOBA, IsoLG will preferentially bind to and therefore be inactivated by 2-HOBA thereby sparing injury to the atrial tissue caused by oxidative stress and its contribution to early recurrence of AF. Early recurrence of AF will be measured by ECGs that are recorded once per day by a smartwatch (Apple Watch, Apple Inc., Cupertino, CA) with additional ECGs recorded by the participant if they experience symptoms of AF, or if the smartwatch alerts the participant of a possible AF episode via its auto-detection AF monitoring algorithm. The Apple Watch's AF algorithm is based on sampling of heart rate and variability and will give an audible alarm if those parameters indicate a possible episode of AF. The smartwatch records a single-lead ECG if the participant touches the watch with their contralateral hand. The day and time of the episode is also stored by the smartwatch. At the end of the 28-day follow-up period, study personnel will review the stored ECGs. Blood will be drawn prior to ablation and on post-procedure Day 1 for measurement of IsoLG-adduct levels. DNA will be extracted to explore a pharmacogenomic interaction with haplotypes at the chromosome 4q25 AF risk locus, which: 1) is strongly associated with the development of AF and the early recurrence of AF after ablation²⁷; and 2) has been reported to be a regulator of an anti-oxidant gene program in response to cardiac injury.²⁸

The proposed double-blind, randomized, placebo-controlled trial of 2-HOBA in patients undergoing AF ablation is designed to address the following Specific Aims:

Specific Aim 1: To test the hypothesis that treatment with 2-HOBA reduces early recurrence of AF (clinical endpoint)

Specific Aim 2: To test the hypothesis that treatment with 2-HOBA reduces circulating levels of IsoLG-adducts (biochemical endpoint)

Specific Aim 3: To explore the idea that genetic variation at the 4q25 (*PITX2*) AF susceptibility locus modulates the clinical and biochemical response to 2-HOBA

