5.0 ENROLLMENT AND RANDOMIZATION

Recruitment and informed consent: Eligible subjects will be identified through EPIC. A member of the study team will request an introduction from the clinical staff. If the patient agrees, a member of the study team will approach the patient in person in Arrhythmia Clinic or by phone prior to AF ablation. Information describing the study, why the research is being done and what will be learned will be provided. The risks as described in this protocol will be delineated. The benefits will be described as general scientific knowledge, along with potential treatment advances. No direct immediate benefit to the subjects is anticipated. Informed consent will be documented with the subject's signature using an IRB-approved consent form for this protocol. An option will be available for phone consent with electronic signature.

Randomization: This will be a double-blind, randomized study. Eligible subjects will be randomized according to a stratified permuted block scheme with a block size of 8. This ensures that the cumulative number of assignments to each treatment (2-HOBA or placebo) will be in balance after each block of assignments had been made. Stratification will be made based on: 1) the planned ablation technique, cyroballoon vs. radiofrequency, 2) paroxysmal vs. persistent atrial fibrillation, 3) *de novo* vs. repeat ablation. A statistician will design the randomization table and enable the randomization tool within REDCap. After a patient enrolls for the study, the study nurse will determine the treatment assignment using the randomization tool in REDCap.

The study drug will be started 3 days prior to ablation. The dose of 2-HOBA will be 750mg three times per day (TID). At least 24 hours in advance, the study nurse will notify IDS to randomize the participant and prepare the study drug. MTI will provide 2-HOBA to the IDS as a 250 mg capsule. MTI will also provide matching

placebo capsules. The study nurse will arrange for the study drug to be given to the participant in-person or mailed. The total duration of the study drug is 31 days (3 days before ablation + 28 days after ablation).

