- A post ablation blood draw will be collected at the conclusion of the AF ablation prior to the central venous catheter removal. We will collect an additional 30 mL blood sample for research, with 10 mL of blood delivered to the Core Laboratory for Cardiovascular Translational and Clinical Research and 20 mL put in green top tubes and delivered to the research laboratory for culturing of monocytes and dendritic cells for measurement of isolevuglandin-adduct levels
- Following ablation, the patient will be extubated while in the operating room and returned to the EP holding room awake and alert.
- After removal of central venous catheters and when the patient is ready to begin eating and drinking, another dose of the study drug will be given.

Encounter 3: Post-ablation day #28

- The participant will be met in either the: 1) VHVI Arrhythmia Outpatient Clinic at the time of their 1-month Post-op Clinical Visit (Medical Center East or One Hundred Oaks locations), or 2) the VHVI Research Room.
- A 10 mL blood sample (divided between purple and blue top tubes) will be delivered to the Core Laboratory for Cardiovascular Clinical and Translational Research.
- The study personnel will record any ECGs recorded from the smartwatch from the day of the ablation until the end of the 28-day of follow-up period
- The study personnel will record remaining pills of either placebo or 2-HOBA at the conclusion of the study
- Participants will be allowed to keep the smartwatch
- Should the participant have required an iPhone as well as the smartwatch, the phone will be returned to the study personnel

Encounter 4: 6 and/or 12 month follow up visits

- Participants undergoing ablation are routinely seen at 6 and 12 months during follow up as part of clinical care
- During these visits, study team personnel may review medical records and meet with participants regarding clinical outcomes of their ablation procedure
- If 6 or 12 month follow up visits are not planned, study personnel may call patients during the 12 month time frame to see if any clinical events have occurred

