7.0 RISKS

Patients undergoing AF ablation are at risk for complications by nature of the procedure. These risks are inherent to the patient population studied here. The risks of obtaining blood samples from phlebotomy of peripheral veins and existing venous lines are minimal.

One risk of donating samples for genetic research may be the release of information that could link the patient to the stored samples and/or the results of the tests run on those samples. The release of this information could cause problems with insurance or future employment. We have mechanisms in place to protect against such risks.

8.0 REPORTING OF ADVERSE EVENTS OR UNANTICIPATED PROBLEMS INVOLVING RISK TO PARTICIPANTS OR OTHERSData and Safety Monitoring Plan

Oversight of the data and safety monitoring plan will be provided by a Data and Safety Monitoring Board (DSMB). The DSMB will meet at least twice a year and review data on adverse events, adverse drug reactions, data quality, and study recruitment. DSMB reports will be sent to the IRB at least yearly.

Data Safety Monitoring Board (DSMB) will be formed to review safety data, study progress, and data quality every 6 months or after enrollment of every 30 subjects, whichever occurs earlier. The DSMB will be chaired by [name], MD, MPH Associate Professor of Medicine, Director, Nonalcoholic Fatty Liver Disease Program, Columbia University – NY Presbyterian Hospital; an external member will be [name], MD, MPH, Professor of Medicine, Brigham and Women's Hospital, Director of the Center for Arrhythmia Prevention, who has expertise in clinical trials of AF; and a biostatistical member, [name], who has expertise in biostatistical review for DSMBs. The DSMB will review all serious adverse events (AEs). Any serious AE will be reported to the DSMB, IRB, and FDA as soon as possible, but not more than three days from the investigators' awareness of the event. Any untoward medical event will be classified as an AE, regardless of its causal relationship with the study.

Reporting of Adverse Events or Unanticipated Problems involving Risk to Participants or Others:

Definitions of adverse events: an adverse event (AE) is "any untoward medical occurrence in a patient or clinical investigation subject administered a pharmaceutical product and which does not necessarily have a causal relationship with this treatment".

Adverse events include:

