Sample size and power (Aim 1): The sample size of this study is based on a logistic regression of the binary primary endpoint of early AF recurrence by the end of follow-up. A total sample size of 162 with 81 in each arm will provide 81% power to detect a reduction in the rate of early recurrence of AF if the event rate is 29% in the treatment arm. This change corresponds to an odds ratio of 0.4 (treatment vs control), which is nearly equivalent to the odds ratio observed in similar trials using colchicine (colchicine OR 0.38)²⁶ at the significance level of 0.046 using a 1-sided Farrington and Manning likelihood score test, and a 48% rate of early recurrence in the placebo (control) group. The estimate 48% rate of early recurrence was extrapolated from our pilot data, which found a 45% rate of recurrence, but did not utilize continuous monitoring as will be performed in our trial. An interim analysis will be performed for superiority after half of the patients (n=40 per group) have completed their 28-day assessment of the primary endpoint at the significance level of 0.006. The final analysis will be performed after all patients have completed their 28-day assessment of the primary point at two-sided significance level of 0.041. Efficacy will be declared early at the interim analysis if the efficacy boundary is crossed ($p < 0.007$). All on-study patients will be followed for efficacy and safety until the planned end-of-follow-up. If the interim analysis indicates that the treatment is not better than the control by 13% (non-binding futility boundary $p > 0.4$), we may close the recruitment into study with regard to any recommendations of DSMB. The O'Brien-Fleming boundaries was used for the alpha- and beta-spending functions to preserve the overall Type I and Type II error.

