provided by the continuous HR monitor provided by the smartwatch. The analysis will be performed using a linear mixed models (LMM) in which the AF burden is assessed weekly during the 4-week (28-day) follow-up period. Same covariates mentioned in the primary analysis will be considered. Additionally, AF burden will also be analyzed in ordinal scale using generalized estimating equation (GEE), ranked based on severity according to increasing AF burden and whether or not a cardioversion was performed. For any missing data in the covariates, we will use a multiple imputation method that incorporates predictive mean matching and flexible additive imputation models as implemented in the aregImpute function in the *Hmisc* R package. The impact of missing data on the validity of results will be examined with a pattern-mixture approach using the R package *SensMice*. This will be done for Aims 1 and 2. Additional secondary analyses will include: 1) multivariable modeling of participants who were excluded from the primary analysis due to the use of colchicine or steroids during the follow-up period (will examine clinical and biochemical endpoints); 2) multivariable modeling with adjustment for 2-HOBA levels for the clinical and biochemical endpoints; 3) multivariable modeling with adjustment for duration of smartwatch use.

Interim Analyses (Aim 1): An interim analysis will be performed by the study team and reviewed by the DSMB. When 50% of the target enrollment is reached testing for an association between 2-HOBA or placebo and significant adverse events (see Ethical Aspects of the Proposed Research for details), superiority and futility will be performed (see above: Sample Size and Power Aim 1). The interim analysis will include early stopping rules for superiority, futility, and harm.

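### The by-arm interim analysis is assigned to the study team, and nothing in the plan limits who sees the result while up to 82 of 162 endpoints are still to come

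*Combined protocol and SAP*

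**What the plan says.** **Who runs the interim.** Section 10.1, Interim Analyses: "An interim analysis will be performed by the study team and reviewed by the DSMB". On scope, the same paragraph states: "The interim analysis will include early stopping rules for superiority, futility, and harm".

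**When.** Section 10.1, Sample size and power: "An interim analysis will be performed for superiority after half of the patients (n=40 per group) have completed their 28-day assessment".

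**Who acts on futility.** The boundary is non-binding. If it is crossed, "we may close the recruitment into study with regard to any recommendations of DSMB".

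**Who the study team is.** Section 5.0, on recruitment: "a member of the study team will approach the patient in person in Arrhythmia Clinic or by phone prior to AF ablation". Section 6.0 (Encounter 2) has the study team set up the watch and show patients how to record ECGs. For the endpoint data the term is study personnel. Section 6.0 (Encounter 3): "The study personnel will record any ECGs recorded from the smartwatch". Section 2.0: "At the end of the 28-day follow-up period, study personnel will review the stored ECGs".

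**Statisticians.** Section 10.0 opens with one biostatistician, who wrote the plan and is in charge of the trial's analysis. Section 8.0 lists a DSMB biostatistical member "who has expertise in biostatistical review for DSMBs", but gives that member no part in producing the interim comparison.

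**Blinding.** Section 5.0 describes a double-blind trial with matching placebo capsules.

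**The concern.** In a double-blind trial, comparative interim results are normally kept from those who conduct it. This plan states the opposite arrangement: the team produces the comparison and the DSMB reviews it. That is a stated rule, not simply an omitted detail.

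Four things are exposed here.

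- **Recruitment.** A team that knows the trend may recruit differently, or with different energy, in the second half.
- **Coaching.** The endpoint depends on recordings that participants make themselves, daily and when prompted by symptoms or an alert. How firmly they are encouraged can change how many recurrences are captured.
- **Final model.** The person directing the primary regression could have seen the arm difference before its form is settled.
- **Futility.** Those who carry out the trial would help decide on a non-binding boundary while holding the result.

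**Working it through.** The point concerns who does what, so the main check sets the sections side by side. The plan gives no figure for it.

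**1. Is there a restriction anywhere?** I looked for four safeguards.

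| Safeguard | Found in the documents |
|---|---|
| Independent or unblinded interim statistician | No. Section 10.0 describes one statistician for the whole trial |
| Closed DSMB report | No. Sections 8.0 and 10.1 give the DSMB review only |
| Limit on who sees arm-level results | No |
| ECG reviewers kept blind to interim results | No. Only the general double-blind statement in Sections 2.0 and 5.0 |

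**2. How many endpoints are outstanding?** Inputs: total 162 and interim at 40 per group (Section 10.1).

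- Analysed at interim: 2 × 40 = 80.
- Outstanding: 162 - 80 = 82, and 82/162 = 50.6%.

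The Interim Analyses paragraph instead times the look at 50% of enrolment, which leaves 162 - 81 = 81 still to enrol. I use the completed-endpoint trigger because it is the more specific.

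**3. Why 82 is a maximum.** Some of the 82 are ablated before any result exists. Section 3.4 plans 1 participant per week and reports 1.375 per week in the pilot. Follow-up is 28 days, or 4 weeks.

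- In follow-up at the cut: 4 × 1 = 4, or 4 × 1.375 = 5.5.
- Not yet ablated at the cut: 82 - 4 = 78 (48.1%), or 82 - 5.5 = 76.5 (47.2%).

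The documents do not say how long analysis and DSMB review take. Assume 4 to 8 weeks with enrolment continuing:

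- At 1 per week: 78 - 4 = 74 down to 78 - 8 = 70 (45.7% to 43.2%).
- At 1.375 per week: 76.5 - 5.5 = 71 down to 76.5 - 11 = 65.5 (43.8% to 40.4%).

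So under that assumption roughly 40% to 46% of the trial would be ablated and coached after a result exists.

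**4. Is the final model really open?** Section 10.1 (Primary Analysis) names treatment plus seven covariates: age, gender, AF type, isolation method, additional lesions, BMI and hours of monitoring. That is 8 terms if all are linear. It also allows splines for three of them and applies a limit of one degree of freedom per 10 of the less frequent outcome. At the planning rates:

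- Events: 81 × 0.48 + 81 × 0.29 = 38.9 + 23.5 = 62.4.
- Allowed degrees of freedom: 62.4/10, or about 6.

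Six is fewer than eight, before any spline. Someone must choose what to drop or simplify, and the plan does not fix that choice in advance.

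**5. Does any design figure depend on this?** No. The stated 81% power comes out at 79.1% to 79.3% with 81 per arm, 48% versus 29% and one-sided 0.046. That is within 2 points, and changing who runs the interim does not alter it.

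**The case against.** The strongest reply is that the natural reader of Section 10.0 would expect the trial biostatistician to run the interim. That person is given no recruiting, watch or ECG role, and could hold the results alone. Access rules are also often set in a DSMB charter, which is not among these documents. Both remarks are fair. They show that a firewall may exist in practice. They do not show that the plan provides one, and the same biostatistician directs the partly open final analysis.

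Four stronger readings are tempting, and the documents do not support them.

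- **That ECG reviewers will know the results.** No section says results circulate to every team member. The text supports only that they could, because nothing prevents it.
- **That the same individuals recruit, coach, read ECGs and analyse.** Section 5.0 speaks of a study team member and Sections 2.0 and 6.0 of study personnel. Nothing establishes that they are the same people.
- **That the final p-value is invalid.** Arm totals do not disclose any participant's assignment. If individual blinding holds, changed recruitment or coaching falls on both arms alike. It may shift the population or event rate without biasing the comparison. Bias by arm would need assignments to be known or guessed. Section 5.0's wording on the study nurse and the randomization tool raises that as a separate question.
- **That the team alone decides whether to stop, or that overriding futility inflates type I error.** The futility sentence refers to DSMB recommendations, and a non-binding futility boundary can be overridden without raising type I error.

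The endpoint also has some structure: a fixed morning recording, automatic alerts and a 30-second criterion. This limits the room for judgement without removing it.

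**Conclusion.** The point holds as a missing safeguard that should be corrected. The plan assigns a comparative interim analysis to the study team and contains no limit on access to the result. The exposure is at most 82 of 162 participants (51%), and about 40% to 46% if only those ablated after a result exists are counted, under the 4-to-8-week assumption. These are headcounts, not effects on the estimate, power or alpha. No such effect has been shown.

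The conclusion rests on reading 'study team' as the protocol uses it elsewhere, and on no separate charter overriding the sentence. If a charter already imposes a firewall, the remaining problem is that the protocol contradicts it.

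**What to change.** Replace the sentence in Section 10.1, Interim Analyses, with text to this effect:

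> The interim comparison will be run by the DSMB biostatistician, or by another statistician with no role in trial conduct or in the final analysis, from a locked data set, and presented in closed DSMB session. The study team will supply analysis code written blind to assignment and will receive only the recommendation to continue or stop. Those who review the ECGs will remain blinded to assignment and to interim results.

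Align the futility sentence in the sample-size paragraph, so that the team acts on the DSMB's recommendation without seeing the comparison. Add a matching line to the DSMB charter.

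The cost is one paragraph and a charter line. The DSMB already has a biostatistical member. The small downside is that whoever runs the comparison must be given the data and the code. Sample size, alpha and boundaries do not change.

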10.2. Aim 2 (Biochemical Endpoint)

Primary hypothesis: The primary endpoint for Aim 2 will be the IsoLG-adduct content of dendritic cells expressed as a percentage (IsoLG-adducted dendritic cells/total dendritic cells x 100). We will test the hypothesis that 2-HOBA reduces the change in IsoLG-adduct levels that occurs with AF ablation (as measured on post-procedure day #1 minus pre-ablation blood samples).

Sample size and power (Aim 2): Our pilot data shows that the change in dendritic cell IsoLG-adduct level is 23% following ablation in our placebo (control) group and we expect the range of possible observed reduction to be 20-40%. With n=81 participants in each arm, the study provides at least 80% power to detect a minimal 22% reduction in IsoLG-adduct level at two-sided significance level of 5%.

Primary Analysis (Aim 2): Our primary analysis will use multivariable linear regression to test whether our primary determinant (2-HOBA versus placebo), significantly reduces the change in IsoLG-adduct levels (continuous), adjusted for baseline pre-ablation IsoLG-adduct level and other potential confounding factors: age, sex, method for pulmonary vein isolation (radiofrequency versus cryo), additional ablation lesions (yes/no), and BMI (continuous). The IsoLG content of dendritic cells adjusted for baseline level will be presented for both treatment arms, together with corresponding 95% confidence intervals (CIs) and p-values will be graphically interpreted using boxplots, partial effect plots, residual plots, etc.

Secondary Analysis (Aim 2): A secondary endpoint will be the IsoLG-adduct level in monocytes. Due to the prohibitively labor-intensive process required to measure IsoLG content in dendritic cells and monocytes, only the pre-ablation and post-procedure day#1 samples will be analyzed for the analysis. However, blood samples from 2 additional time points (baseline and post-procedure day #28) will be available for pharmacokinetic

analysis and secondary analysis of other serological markers. These will include malondialdehyde and other biomarkers of oxidative stress.

10.3. Aim 3 (Exploratory Genomics): This aim will use the 162 subjects enrolled in Aims 1 and 2. DNA will be extracted and genotyping will be performed on a GWAS chip that includes the 3 SNPs located at chromosome 4q25 that are independently associated with AF risk (rs2200733, rs17570669, and rs3853445).³⁴ The 4q25 GRS will be a weighted score calculated by using the OR for AF multiplied by the number of risk alleles present from each of the 3 independent 4q25 SNPs. We hypothesize that a statistically significant interaction will exist between the 4q25 GRS and the treatment group (2-HOBA or placebo) for an association with our clinical and biochemical endpoints. In Aim 3, we will test for an interaction between the 4q25 GRS and the treatment group for an association with the primary clinical endpoint (early recurrence of AF). Adjustment will be made for the covariates used in Aim 1. We will then add the 4q25 GRS to the multivariable linear regression model used in Aim 2 and test whether there is a statistical interaction between the GRS and the treatment group for an association with the primary biochemical endpoint (change in dendritic cell IsoLG-adduct level with ablation) by comparing models with and without the interaction term using likelihood ratio test. The added predictive value of 4q25 GRS and the interaction of GRS and treatment will be evaluated by comparing nested models with and without the predictor with regard to c statistics and the integrated discrimination improvement. Models involving 4q25 GRS will be internally validated using the aforementioned bootstrap method for the evaluation and correction of potential optimism in the performance of the model by balancing the bias and variance in the prediction error. All statistical tests will be considered significant at two-sided 5% level.

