3.4. A pilot study demonstrates that AF ablation increases IsoLG adduct levels

In preparation for this trial, a pilot study (IRB #171722) was conducted to demonstrate the feasibility of the study protocol, demonstrate that IsoLG-adduct levels increase following AF ablation, and generate preliminary data for the power/sample size analysis. These measurements are made using a cellular system (since IsoLG adducts are not free in the circulation), and has used IsoLG measurements in monocytes and dendritic cells (DC).³⁰ Over an 8-week period, 11 subjects who met the eligibility criteria for our proposed clinical trial were prospectively enrolled and underwent AF ablation. The data from our pilot study support the following conclusions:

1. The rate of participant enrollment was sufficient to meet the enrollment target of this proposal. We have proposed to enroll 1 participant per week to accrue 162 participants over 36 months. We enrolled 1.375 participants per week in the pilot study.
2. AF ablation resulted in a statistically significant increase in circulating IsoLG-adduct levels. IsoLG-adduct levels were measured in blood samples collected pre-ablation and on post-procedure day #1. IsoLG-adduct levels increased in 82% (9/11) of subjects, and the mean increase was 23% in DCs (Pre: $41 \pm 16\%$ vs. Post: $63 \pm 17\%$; $P=0.02$; **Figure 4, top panel**) and 21% (Pre: $38 \pm 19\%$ vs. Post: $59 \pm 18\%$; $P=0.04$) in monocytes following ablation.
3. There was an early recurrence of AF in 45% of participants (5/11). This demonstrates that, similar to other published reports, early recurrence of AF is common in our study population and is sufficient to power the primary endpoint of Aim 1, which is AF recurrence within 28-days following ablation (**Figure 4, bottom panel**). This is comparable to the early recurrence rate of AF from numerous other published reports, which is $\sim 50\%$.^{21,23}

[figure not shown]

Figure 4: (Top) There is a significant increase in the proportion of dendritic cells containing IsoLG-adducts from pre-ablation to post-operative day #1 (POD1; $P=0.02$). **(Bottom)** 45% of participants had an early recurrence of AF within our proposed 28-day monitoring period.

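### The Aim 2 endpoint uses a post-procedure Day 1 sample, but the Section 6 schedule has no Day 1 draw and takes the post-ablation assay sample at the end of the procedure

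*Combined protocol and SAP*

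**What the plan says.** Three places in the combined protocol and SAP put the post-ablation measurement on the day after the procedure.

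- Section 2.0: "Blood will be drawn prior to ablation and on post-procedure Day 1 for measurement of IsoLG-adduct levels".
- Section 10.2, primary hypothesis: the change is taken "as measured on post-procedure day #1 minus pre-ablation blood samples".
- Section 10.2, secondary analysis: because the assay is laborious, "only the pre-ablation and post-procedure day#1 samples will be analyzed for the analysis".

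The pilot in Section 3.4 used the same interval: "IsoLG-adduct levels were measured in blood samples collected pre-ablation and on post-procedure day #1", "and the mean increase was 23% in DCs". Section 10.2 carries that 23% forward as the control-group change. It states at least 80% power, with 81 per arm and a two-sided 5% level, to detect a 22% reduction.

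Section 6.0 sets out a different schedule. Under Encounter 2, the day of ablation, "A post ablation blood draw will be collected at the conclusion of the AF ablation prior to the central venous catheter removal". Of that blood, "20 mL put in green top tubes and delivered to the research laboratory for culturing of monocytes and dendritic cells" for the adduct assay. The next heading is "Encounter 3: Post-ablation day #28", and the Day 28 blood goes only to the core laboratory.

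**The concern.** The endpoint definition and the visit schedule name different post-ablation samples. Staff working from Section 6 would collect a culture sample that Section 10.2 does not list for assay, and would not collect the one it requires. A Day 1 sample that was not drawn cannot be obtained later.

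Two things are at stake. The first is whether the Aim 2 endpoint can be computed as defined. The Aim 3 biochemical test in Section 10.3 shares this problem, because it adds the genetic score and its interaction with treatment to the Aim 2 model and uses the same change as outcome. The second is the basis of the Aim 2 power statement, whose expected change was observed over a different interval from the one Section 6 would sample.

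**Working it through.** **Step 1. Compare the draws.** Section 6 lists three research draws. Section 10.2 needs two culture samples.

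| Time | Draw in Section 6? | Culture tubes for the adduct assay? | Needed for the Aim 2 endpoint? |
|---|---|---|---|
| Before ablation | Yes, 30 mL | Yes, 20 mL | Yes |
| End of ablation, before catheter removal | Yes, 30 mL | Yes, 20 mL | Not listed |
| Post-procedure Day 1 | No | No | Yes |
| Day 28 | Yes, 10 mL | No, core laboratory only | No |

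Section 6 therefore supplies one of the two samples needed.

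**Step 2. Could this be a difference of labels?** Section 6 places the draw on the day of ablation, through the procedural catheters, and lists it before extubation and return to the holding room. Nothing in the documents says that this draw counts as Day 1 or replaces it.

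**Step 3. Can the stated 80% be reproduced?** Inputs from Section 10.2 are 81 per arm, two-sided 5% and a 22% reduction. With a normal approximation, 80% power requires

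effect / SD = (1.960 + 0.842) × sqrt(2/81) = 0.440.

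Section 10.2 plans a regression adjusted for the pre-ablation level, so the SD here is the residual SD after that adjustment. The documents do not give it; Section 3.4 gives only the SDs of the pilot levels, 16 before and 17 after. Nor do they say what the 22% is a percentage of. The largest residual SD that still gives 80% power depends on the reading:

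- 22% of the 23-point rise: 0.22 × 23 = 5.06 points; 5.06 / 0.440 = 11.5.
- 22% of the post-ablation level of 63: 0.22 × 63 = 13.86 points; 13.86 / 0.440 = 31.5.
- 22 absolute points: 22 / 0.440 = 50.0.

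The 80% can thus be neither reproduced nor refuted, even at Day 1.

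**Step 4. Does the 80% carry over to the end of the procedure?** The 23-point rise and both SDs come from the pilot's pre-ablation and Day 1 samples in 11 subjects. The documents report no mean and no SD for an end-of-procedure sample. Power at that time cannot be computed from them.

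**The case against.** The strongest reply is that the plan does prescribe the Day 1 draw. Section 2 says so, Section 10.2 names that sample twice, and Section 6 may simply have omitted it. If sites draw on Day 1 anyway, the endpoint can be computed and the planned time point is not in doubt. This stands in part. It makes the consequence conditional on Section 6 being followed, and a reader should not infer that Day 1 samples were in fact missed. Nor do the documents support a charge that the time point is left open to be chosen from the data. Under Section 6 alone there is only one post-ablation culture sample, and if both are drawn, Section 10.2 says which is assayed. The conflict remains, because Section 6 is the operational schedule and it sends a different sample for the same assay.

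A reader might also infer that Aim 2 is underpowered. That does not follow. If the pilot P=0.02 is assumed to come from a paired t-test in 11 subjects (t = 2.764), the SD of the change is 23 × sqrt(11) / 2.764 = 27.6. An unadjusted comparison of changes for a 5.06-point effect then has about 22% power, with 0.22 as a share of the 23-point rise. But that SD implies a pre-post correlation of (16² + 17² − 27.6²) / (2 × 16 × 17), about −0.40, which itself casts doubt on the assumption. The planned baseline adjustment would give a residual SD of 17 × sqrt(1 − 0.40²) = 15.6 and power of about 54%. If the 22% means absolute points, power is essentially 100%. The documents settle neither the SD nor the reading.

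Finally, Section 10.1 calls Aims 2 and 3 exploratory. This limits the severity. It does not remove the conflict, since Section 10.2 still sets a primary endpoint and a powered test.

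**Conclusion.** The point holds as an internal contradiction that should be fixed. On the Section 6 schedule, one of the two samples needed for the Aim 2 primary endpoint is not collected, so that endpoint and the Aim 3 biochemical interaction test cannot be computed as defined. The stated 80% rests on a Day 1 pilot change and has no documented support at the end of the procedure; its true value there is unknown, not shown to be low.

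The conclusion assumes that Section 6 governs what is drawn and that no separate instruction adds a Day 1 sample; none appears in the documents. Confidence in the contradiction is high, because it rests on the text and not on a calculation. The Aim 1 clinical endpoint, its sample size and its interim rules are untouched.

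**What to change.** Before unblinding, make Sections 2, 6 and 10.2 name the same post-ablation assay sample, and record the actual time of each draw. Section 10.3 then follows by reference. There are two ways to do this, and both keep two assays per participant.

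1. Redefine the change as end-of-procedure minus pre-ablation. This is a change of wording that uses blood Section 6 already collects. The Day 1 pilot change must then be withdrawn as the basis for the 80%. The cost is that no pilot data exist at that time.
2. Add a Day 1 culture draw to Section 6. This keeps the pilot's interval. It adds a contact that Section 6 does not list, and it cannot recover Day 1 values for participants already sampled only under Section 6. The end-of-procedure draw need not be dropped, since Section 10.2 limits what is assayed and not what is drawn.

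The sponsor should first establish which samples have been taken so far, because the documents do not show this. Whichever option is chosen, the restated Aim 2 power should give the residual SD after baseline adjustment, with its source, and say what the 22% refers to. That costs only the text.
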